- Mean and median total dose: Total dose (in mg) is calculated by the number of active injections taken during the treatment period multiplied by dose. For participants in the Safety Population who were randomized to lebrikizumab 250 mg Q4W or Q2W, or participants in the MPP who received lebrikizumab 250 mg Q4W or Q2W, the total dose (in mg) taken during the Induction Period or the Maintenance Period will be calculated as follows: *Total lebrikizumab dose=Total number of active injections (including loading doses, if any) received in the Induction Period or the Maintenance Period ×250.*
- Total number of injections received will be derived based on the response to the question “Was dose administered?” on the *Exposure as Collected* eCRF page.

The exposure for the All Lebrikizumab Safety Population during the Combined Induction and Maintenance Periods will be calculated as (Date of last study visit during Treatment Period – Date of first lebrikizumab injection +1 day) calculated for each treatment period where the participant receives lebrikizumab and then summed together (this excludes the duration of time that participants are receiving placebo during the Maintenance Period).

The exposure for the All Lebrikizumab Safety Population during the Combined Induction and Maintenance Periods plus Follow up Period will be calculated as the time between the first dose of lebrikizumab and the study treatment disposition visit plus any follow-up period.

4.6.2. Adverse Events

A TEAE is defined as an event that first occurred or worsened in severity after baseline. The MedDRA Lowest Level Term (LLT) will be used in the treatment-emergent computation. The maximum severity for each LLT during the baseline period defined in Section 4.1.1 for the Induction Period and Section 4.1.2 for the Maintenance Period will be used as baseline. The

Treatment Period will be used as the post-baseline period for the analysis. For events with a missing severity during the baseline period, it will be treated as 'mild' in severity for determining treatment-emergence. Events with a missing severity during the post-baseline period will be treated as 'severe' and treatment-emergence will be determined by comparing to baseline severity. For events occurring on the day of first taking study medication, it will be assumed to be post-treatment.

The planned summaries for adverse events are provided in the table below, and are described more fully in compound level safety standards and in the adverse event-related PhUSE white paper [Analysis and Displays Associated with Adverse Events: Focus on Adverse Events in Phase 2-4 Clinical Trials and Integrated Summary Document (PhUSE 2017)].

Summary tables as described in the table below will be presented for the following periods/analysis populations as indicated. Summary tables will include the number and percentage of participants reporting an event. For events that are gender-specific (as defined by MedDRA), the number of participants at risk will include only participants from the given gender.

- Induction Period (Safety Population, S)
- Maintenance Blinded Period (Maintenance Primary Population, M)
- Combined Induction and Maintenance Periods, Combined Induction and Maintenance Periods Plus Follow-Up Period (selective analyses) (All Lebrikizumab Safety Population, A)

Summary Tables/Listing Related to Adverse Events

Analysis	Population
Overview of AEs	S, MPP, MSP, A
Summary of TEAE by PTs	S, MPP
Summary of TEAE by PTs occurring in $\geq 1\%$ of participants	S, MPP
Summary of TEAE by PTs within SOC	S, MPP, A
Summary of TEAE PTs by maximum severity	S, MPP
Summary of SAE by PTs within SOC	S, MPP, A
Summary of AEs leading to treatment discontinuation by PTs within SOC	S, MPP, A
Summary of TEAE possibly related to study drug by PTs within SOC	S, MPP
Listing of SAEs (including Death)	ITT
Listing of primary AEs leading to study treatment discontinuation	ITT
Listing of AE (including AEs in the Maintenance Period and the Follow-Up Period)	S

Abbreviations: A = All Lebrikizumab Safety Population; AE = adverse event; ITT = Intent-to-Treat; MPP = Maintenance Primary Population; MSP = Maintenance Secondary Population; PT = Preferred Term; SAE = serious adverse event; S = Safety Population; SOC = System Organ Class; TEAE = treatment-emergent adverse event.

Statistical comparisons will be performed for Safety Population using Fisher's exact test. OR will be provided.

4.6.2.1. Common Adverse Events

The number and percentages of participants with TEAEs will be summarized by treatment using MedDRA Preferred Term (PT) for the common TEAEs (occurred in $\geq 1\%$ before rounding in total lebrikizumab column in the table).

4.6.2.2. Deaths, Other Serious Adverse Events, and other Notable Adverse Events

The number and percentage of participants reported with an SAE during the treatment period will be summarized by treatment using MedDRA PT. A listing of SAEs will be provided.

The number and percentage of participants who permanently discontinued from study treatment due to an AE (including AEs that led to death) during the treatment period will be summarized by treatment using MedDRA PT. Events will be ordered by decreasing frequency in all treatment groups.

4.6.3. Additional Safety Assessments

4.6.3.1. Clinical Laboratory Evaluation

As described more fully in compound level safety standards and in the laboratory-related PhUSE white papers (PhUSE 2013; PhUSE 2015), the clinical laboratory evaluations will be summarized as described in the table below. Hormone analytes are summarized/Plotted similarly for adolescent participants.

Analysis for Clinical Laboratory Evaluations

Analysis	Population
Box plots of observed values by visit	S, MPP, A
Box plots for change values by visit	
Change from baseline to last observations. ANCOVA model with treatment and baseline value in the model.	S, MPP
Scatter plots of baseline-by-maximum values and baseline-by-minimum values	S, MPP
Treatment-emergent abnormal high lab values (i.e., participants shifting from a normal/low maximum baseline value to a high maximum post-baseline value) or abnormal low lab values (i.e., participants shifting from normal/high minimum baseline value to a low minimum post-baseline value)	S, MPP, A
Shift tables showing the number of participants who shift from each category of maximum (minimum) baseline observation to each category of maximum (minimum) post-baseline observation. Categories may be low, normal, or high with cut-offs defined in the compound level safety standards.	S, MPP
Listing of abnormal findings for laboratory analyte measurements, including qualitative measures	S

Abbreviations: A = All Lebrikizumab Safety Population; ANCOVA = analysis of covariance; MPP = Maintenance Primary Population; S = Safety Population.

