#### **9.4.3.2. Secondary Analyses**

For secondary binary efficacy and health outcome endpoints during the Induction Period, the CMH test will be used to compare the treatment groups while adjusting for the stratification factors (disease severity: IGA 3 versus 4, and age: adolescent participants  $\geq 12$  to  $< 18$  years versus  $\geq 18$  years).

Treatment comparisons of secondary continuous efficacy and health outcome endpoints during the Induction Period will be made using an analysis of covariance with the following in the model: treatment group, baseline value, and stratification factors.

Efficacy, health outcome, and safety measures during the Maintenance Period will be summarized using descriptive statistics by treatment group.

More details will be specified in the SAP.

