Maintenance W20-64 Escape Population	Participants in MPP or MSP who escaped to lebrikizumab 250 mg Q2W due to EASI-50 non-response at Weeks 20, 24, 28, 32, 36, 40, 44, 48, 52, 56, 60 or 64. Selective efficacy analyses for the Maintenance Period will be conducted on the Maintenance W20-64 Escape Population to assess whether these participants re-gain EASI-50 response or achieve a higher level of response (for example, EASI-75) following re-treatment.
All Maintenance Population	Participants who entered the Maintenance Period and received at least one dose of study intervention during the Maintenance Period.
All Lebrikizumab Safety Population	All randomized participants who received at least 1 dose of lebrikizumab treatment during the Combined Induction and Maintenance Periods including participants who were randomized to placebo at baseline visit (Visit 2, Week 0) and moved to the Escape Arm at Week 16 or later visits in the Maintenance Period. Safety analyses for the Combined Induction and Maintenance Periods will be conducted on the All lebrikizumab Safety Population. Selective safety analyses for the Combined Induction and Maintenance Periods plus the Follow-Up Period will be conducted on the All Lebrikizumab Safety Population.
Pharmacokinetic Analysis	All participants who received at least 1 dose of lebrikizumab and have at least 1 evaluable PK sample.

Abbreviations: EASI-75 = $\geq 75\%$ reduction from baseline in Eczema Area and Severity Index IGA = Investigator's Global Assessment; Q2W = every 2 weeks; Q4W = every 4 weeks; W = Week.

Treatment Groups and Comparisons for Each Study Period and Analysis Population

Study Period	Analysis Population	Treatment Groups	Abbreviation	Inferential Comparisons When Applicable
Induction Period	ITT; Safety; PPS	Placebo; Lebrikizumab 250 mg Q4W; Lebrikizumab 250 mg Q2W; Total	PBO; LEB250Q4W; LEB250Q2W; Total	LEB250Q4W vs PBO; LEB250Q2W vs PBO
Maintenance Blinded Period	MPP	Lebrikizumab 250 mg Q4W_Res/ Lebrikizumab 250 mg Q4W; Lebrikizumab 250 mg Q2W_Res/ Lebrikizumab 250 mg Q4W; Lebrikizumab 250 mg Q2W_Res/ Lebrikizumab 250 mg Q2W; Total	LEB250Q4W_Res/ LEB250Q4W; LEB250Q2W_Res/ LEB250Q4W; LEB250Q2W_Res/ LEB250Q2W; Total	No Between-Group or Overall Comparisons
Maintenance Blinded Period	MSP	Placebo_Res/Placebo	PBO_Res/PBO	No Between-Group or Overall Comparisons

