4.1.2.1. Maintenance Primary and Secondary Population

The number and percentage of participants achieving or maintaining categorical efficacy and health outcome responses will be summarized by treatment group for all scheduled visits, including Week 68.

Each continuous efficacy and health outcome measure score and the change from baseline (or percentage improvement) will be summarized by treatment group at all scheduled visits during the Maintenance Period, including Week 68 using descriptive statistics (n, mean, SD, median, minimum, and maximum). No inferential statistics will be provided for these populations.

For the MPP, the KM product limit method will be used to estimate the survival for time to event analyses (e.g., time to loss of IGA score of 0 or 1, or loss of EASI-50). A KM plot of the time to event by treatment group may be provided.

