4.6. Safety Analyses

The planned analyses of safety data will be performed with an intent to maintain consistency with compound level standard safety analyses. These standards are based on internal standards which were informed by Clinical Data Interchange Standards Consortium (CDISC) standards, regulatory guidance (for example, FDA Clinical Review Template), and cross-industry standardization efforts (for example, Pharmaceutical Users Software Exchange [PhUSE] white papers from the Standard Analyses and Code Sharing Working Group provided in the PhUSE Computational Science Deliverables Catalog).

Safety evaluations will be based upon the following safety analysis populations with their associated study periods, unless specified otherwise:

- Safety Population (Induction Period),
- MPP (Maintenance Blinded Period), and
- All Lebrikizumab Safety Population (Combined Induction and Maintenance Periods, and Combined Induction and Maintenance Periods plus Follow-Up Period [selective analyses]).

These analysis populations, treatment groups, associated study periods, and the comparisons for each analysis population are fully defined in Section 3.

For document writing purposes for safety, tests with two-sided p-values less than 0.05 will be referred to as having strong statistical evidence for a treatment difference, unless otherwise noted. However, p-values should not be over-interpreted for these safety analyses. Except for pre-specified hypotheses, they correspond to data-driven hypotheses and hence are only useful as a flagging mechanism.

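### The SAP laboratory table assigns a between-treatment ANCOVA to the Maintenance Primary Population, for which Section 3 allows no comparisons

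*SAP*

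**What the plan says.** The disputed row is in the laboratory analysis table of SAP 4.6.3.1 and concerns laboratory change to the last observation. It specifies "ANCOVA model with treatment and baseline value in the model", and its population column lists S and MPP. The table's footnote spells these out: "MPP = Maintenance Primary Population; S = Safety Population".

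Other parts of the plan say something different about the MPP:

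- **SAP Section 3**, in the table of treatment groups and comparisons, has a column headed "Inferential Comparisons When Applicable". The MPP entry for the Maintenance Blinded Period is "No Between-Group or Overall Comparisons".
- **SAP 4.6** says that the safety populations, their treatment groups, their periods "and the comparisons for each analysis population are fully defined in Section 3".
- **SAP 4.1.2.1**, on the MPP and the Maintenance Secondary Population, says "No inferential statistics will be provided for these populations". That section mainly describes efficacy outputs.
- **Protocol 9.4.3.2** says "Efficacy, health outcome, and safety measures during the Maintenance Period will be summarized using descriptive statistics by treatment group".

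In the general text, the laboratory ANCOVA appears only in SAP 4.1.1, which covers the Induction Period. SAP 4.9, which lists changes from the protocol, mentions no inferential laboratory analysis in the Maintenance Period.

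**The concern.** The row and Section 3 give a programmer opposite instructions. If the row is followed, the treatment term spans the three MPP groups: Q2W responders kept on Q2W, Q2W responders switched to Q4W, and Q4W responders kept on Q4W.

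Only the first two groups are formed by re-randomisation at Week 16. The third consists of participants randomised to Q4W at Week 0 who responded and continued. Comparing them with either Q2W-responder group compares people selected by response to different regimens. The Maintenance safety baseline is also normally the Week 16 value (SAP 4.1.2), taken after 16 weeks on those regimens. Randomisation therefore does not protect such a contrast.

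SAP 4.6 describes safety p-values under 0.05 in terms of strong evidence. In this setting, that description could attach to a difference caused by selection.

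**Working it through.** The plan states no figure on this point, so there is none to reproduce. The check is a comparison of texts, with two small calculations for scale.

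**Step 1. Which text is the outlier?**

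| Place | Position on between-group inference in the MPP |
|---|---|
| SAP 4.6.3.1, ANCOVA row | Model with a treatment term, MPP listed |
| SAP Section 3 | None |
| SAP 4.6 | As in Section 3 |
| SAP 4.1.2.1 | None (mainly efficacy text) |
| Protocol 9.4.3.2 | Descriptive only, safety named |
| SAP 4.1.1 | Laboratory ANCOVA placed under the Induction Period |
| SAP 4.6.2, adverse events | MPP tables planned, but statistical comparisons specified only for the Safety Population |
| SAP 4.9 | No departure from the protocol declared |

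The ANCOVA row stands alone. SAP 4.6 and Section 3 together are the firmest contrary text, because they concern safety populations directly.

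**Step 2. How are the three groups formed?** Protocol 4.1 and 6.3 re-randomise Q2W responders 1:1 to Q2W or Q4W. Q4W responders stay on Q4W. Of the three possible pairs, only Q2W/Q2W versus Q2W/Q4W is a randomised contrast.

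Illustrative sizes use the planned allocation and the assumed EASI-75 rates in SAP Section 5:

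- Q2W responders: 120 × 0.58 = 69.6, so 69.6 / 2 = 34.8 in each re-randomised group.
- Q4W responders: 80 × 0.53 = 42.4.
- Share not re-randomised at Week 16: 42.4 / (69.6 + 42.4) = 42.4 / 112.0 = 0.379, or about 38%.

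These counts use EASI-75 alone. IGA 0 or 1 also qualifies a participant as a responder, so at these rates the group sizes are on the low side. The third group is therefore a substantial part of the MPP.

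**Step 3. How many chance flags per contrast?** Protocol Appendix 2 lists 13 haematology, 20 chemistry and 4 lipid analytes, so 13 + 20 + 4 = 37. With no true effect and a two-sided 5% level, the expected number of flags for one contrast per analyte is 37 × 0.05 = 1.85, about 1.9. This expectation does not require independence between analytes. It is conditional on tests being run, which the row does not state.

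**The case against.** The strongest reply is that the governing text already excludes a test. The row names a model but no p-value, contrast or pair of groups. SAP 4.6 hands comparisons to Section 3, and Section 3 gives none. The row may be a shared template, or it may intend only least squares means. It also says that fuller descriptions are in the compound level safety standards, which are not available here and may settle the matter. This stands as far as it goes: the documents do not establish that an MPP test will be run. However, the SAP gives no rule of precedence between this row and Section 3, and an ANCOVA with a treatment term ordinarily yields a treatment test.

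A reader might also draw four stronger conclusions that the documents do not support:

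- **That the Q4W group is not randomised.** It was randomised at Week 0. It was not re-randomised at Week 16, and that is the accurate statement.
- **That the plan implies about 5.6 false flags.** That figure is 37 × 3 × 0.05 = 5.55 and needs three pairwise MPP contrasts per analyte. No section specifies them. Multiplicity is also not the defect here, because Safety Population laboratory tests have the same expected count per contrast.
- **That p-values below 0.05 would be taken as established findings.** SAP 4.6 goes on to warn against reading too much into safety p-values. Apart from pre-specified hypotheses, it confines them to flagging.
- **That follow-up is unequal across groups.** MPP data do stop at escape, so the last observation could fall at different times. Nothing in the documents shows or estimates a difference between groups.

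**Conclusion.** The inconsistency is real and small. The MPP entry in the ANCOVA row of SAP 4.6.3.1 contradicts SAP Section 3, SAP 4.6 and Protocol 9.4.3.2. The consequence depends on the row being programmed as it reads. In that case, contrasts involving the Q4W responders condition on a post-randomisation response and would make poor safety flags. About 1.9 chance flags would also be expected per contrast, assuming all 37 analytes are tested at 5%.

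The effect is confined to safety flagging in the Maintenance Period. The co-primary and secondary analyses and the Induction Period safety comparisons are untouched.

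**What to change.** In the laboratory table of SAP 4.6.3.1, change the population for the ANCOVA row from S and MPP to S only. Add that MPP laboratory change from baseline is summarised descriptively by treatment group, as Section 3 implies. Check that the compound level safety standards and the table specifications carry the same restriction.

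The cost is one table cell and one sentence, with no new data and fewer outputs. Little is lost, because the same table already plans shift tables and treatment-emergent abnormality summaries for the MPP.

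Keeping a test restricted to the two re-randomised groups is not recommended as the default. It would be a randomised contrast, but it would keep the last-observation endpoint and the cut-off at escape. It would also require changes to Section 3, 4.1.2.1 and 4.9.

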4.6.3.2. Vital Signs and Other Physical Findings

As described more fully in compound level safety standards and in the laboratory-related PhUSE white papers (PhUSE 2013; PhUSE 2015), vital signs will be summarized similarly to the

clinical laboratory evaluation as described in the table below. For vital signs, treatment-emergent low and high are based on a combination of a specified value and a change or percentage change for adults and adolescents as defined in the compound level safety standards.

Analysis Related to Vital Signs

Analysis	Population
Box plots for observed values by visit	S, MPP, A
Box plots for change from baseline values by visit	S, MPP, A
Scatterplots of baseline-by-maximum values and baseline-by-minimum values	S, MPP
Tables with the number and percentage of participants who shift from normal/high to low (i.e., treatment-emergent low) and the number and percentage of participants who shift from normal/low to high (i.e., treatment-emergent high). The limits are defined in the compound level safety standards.	S, MPP, A

Abbreviations: A = All Lebrikizumab Safety Population; MPP = Maintenance Primary Population; S = Safety Population.

4.6.3.2.1. Adolescent Standardized Growth

Weight, height, and BMI data will be merged to the Centers for Disease Control and Prevention (CDC) standard growth data (released in 2000) by age and gender in order to compare participants' growth with the standard. Z-score, and standardized percentile of weight, height, and BMI at each visit will be calculated and compared to the 2000 CDC growth charts. Because of the short duration of controlled period and the small number of adolescent participants, only All Lebrikizumab Safety Population will be described during the Combined Induction and Maintenance Periods.

The z-score and percentile calculations are based on algorithms and data provided by the National Center for Health Statistics. The details are provided in the CDC website (<https://www.cdc.gov/nccdphp/dnpao/growthcharts/resources/sas.htm>) (CDC resources page [WWW]).

Height and weight may also be merged to the Japanese children standard growth data issued by the Japanese Association for Human Auxology to compare adolescent participants' growth with the standard (Isojima et al. 2016).

The following summaries and plots will be provided:

Analysis Related to Adolescent Standardized Growth

Analysis	Population
Summaries for baseline, mean change of actual measure, z-score and standardized percentile of weight, height, and BMI.	A
Scatter plot of participants' mean weight, height, and BMI standardized percentile versus lebrikizumab exposure time	A

Abbreviations: A = All Lebrikizumab Safety Population; BMI = body mass index.

4.6.3.3. Immunogenicity

An individual sample is potentially examined multiple times in a hierarchical procedure to produce a sample anti-drug antibody (ADA) assay result and may yield a sample neutralizing

ADA (NAb) assay result. Treatment-emergent ADA (TE-ADA) are defined as those with a titer 2-fold (1 dilution) greater than the minimum required dilution if no ADAs were detected at baseline (treatment-induced ADA) or those with a 4-fold (2 dilutions) increase in titer compared to baseline if ADAs were detected at baseline (treatment-boosted ADA). A participant is considered TE-ADA positive when at least 1 post-baseline ADA sample meets the definition of TE-ADA.

Compound level safety standards will be followed in the analyses of immunogenicity. Listings of immunogenicity assessments will be provided for the Safety Population. The summary of TE-ADA and NAb status will be produced for the 3 populations (i.e., Safety Population for the Induction Period, MPP for the combined Induction and Maintenance Periods, and All Lebrikizumab Safety Population for the combined Induction and Maintenance Periods plus Follow-Up Period), where the post-baseline period for reporting is the same as described for AEs in Section 4.6.2. Additional assessments of the relationship between immunogenicity and efficacy/safety may be performed in this study.

